14.1 Adverse Events

An adverse event (AE) is any untoward medical occurrence in a subject receiving study drug and which does not necessarily have a causal relationship with this treatment. For this protocol, the definition of AE also includes worsening of any pre-existing medical condition. An AE can therefore be any unfavorable and unintended or worsening sign (including an abnormal laboratory finding), symptom, or disease temporally associated with the use of BMX-001, whether or not related to use of the BMX-001. Abnormal laboratory findings without clinical significance (based on the Pl's judgment) should not be recorded as AEs, but laboratory value changes that require therapy or adjustment in prior therapy are considered adverse events.

From the time the subject signs the informed consent form through the End of Treatment visit (as defined in the section titled End of Treatment), all AEs must be recorded in the subject medical record and adverse events case report form.

AEs will be assessed according to the CTCAE version 4.03. If CTCAE grading does not exist for an AE, the severity of the AE will be graded as mild (1), moderate (2), severe (3), life-threatening (4), or fatal (5).

Attribution of AEs will be indicated as follows:

- Definite: The AE is clearly related to the study drug
- Probably: The AE is likely related to the study drug
- Possible: The AE may be related to the study drug
- Unlikely: The AE is doubtfully related to the study drug
- Unrelated: The AE is clearly NOT related to the study drug

14.1.1 Reporting of AEs

BioMimetix JV, LLC, should be notified of all treatment-related adverse events on a regular basis (to be agreed upon by the study team and BioMimetix JV, LLC).

14.2 Serious Adverse Events

An AE is considered "serious" if in the opinion of the investigator it is one of the following outcomes:

- Fatal
- Life-threatening
- Constitutes a congenital anomaly or birth defect
- A medically significant condition (defined as an event that compromises subject safety or may require medical or surgical intervention to prevent one of the three outcomes above).

- Requires inpatient hospitalization or prolongation of existing hospitalization.
- Results in persistent or significant incapacity or substantial disruption to conduct normal life functions.

Reports of these should be made to [name], PhD, at [contact], or [contact] (cell) with the Clinical Trial Manager on carbon copy.

14.2.1 Reporting of SAEs

Only adverse events that the Sponsor determines to be serious, unanticipated, and related or possibly/probably (i.e., more likely than not) related to the research must be reported to the appropriate IRB. Those adverse events will be submitted in the applicable IRB and sponsor, according the following guidelines:

- Report within 24 hours of learning about any subject's death that was unanticipated and more likely related to the research than unrelated;
- Report within 5 business days of learning about any serious, unanticipated, and related or possibly/probably related adverse event; that was more likely related to the research than unrelated.
- Report within 10 business days of learning about any other SAE that does not meet the above criteria.

The Sponsor must report to the FDA, in an IND safety report, any suspected adverse reaction that is both serious and unexpected. Before submitting this report, the sponsor needs to ensure that the event meets all three of the definitions contained in the requirement:

- Suspected adverse reaction (i.e., there is a reasonable possibility that the drug caused the adverse event)
- Serious
- Unexpected

If the adverse event does not meet all three of the definitions, it should not be submitted as an expedited IND safety report.

The Sponsor is required to report to the FDA all IND Safety reports in writing within 15 days (7 days for unexpected fatal or life-threatening suspected adverse reaction). The FDA Form 3500A can be found on the FDA website, www.fda.gov. All other adverse events will be reported to the FDA in the Annual Report.

The sponsor is responsible for safety reporting to the FDA and for compliance with all applicable laws and regulations pertaining to adverse events. To ensure patient safety each study treatment-related serious adverse event will also be reported to BioMimetix JV, LLC, within 24 hours by the Principal Investigator. Follow-up information on these events shall also be reported to BioMimetix JV, LLC, within 24 hours. Follow-up information may include hospital admission records, discharge summaries and autopsy reports, where applicable.

In addition, the Principal Investigator shall also make an accurate report to the reviewing Institutional Review Board (IRB) on any serious and unexpected AE per local guidelines.

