11.11 Dose-Limiting Toxicity (DLT)

Toxicities will be graded according to the NCI CTCAE version 4.03 criteria. DLTs will be defined as any of the following events that are at least (possibly, probably, or definitely) attributable to BMX-001 during the study. The DLT period includes from the start of BMX-001 through 4 weeks after CRT concludes.

A dose limiting toxicity is defined as an adverse event or laboratory abnormality that is: a) assessed as unrelated to disease progression, intercurrent illness, or concomitant medications; b) occurs during and/or following the first dose of BMX-001; and c) meets any of the following criteria:

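### Section 14.2.1 contradicts itself on SAE deadlines: events rated unrelated have no 24-hour route to the sponsor, and the limit for a possibly related SAE is ambiguous

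*Combined protocol and SAP*

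**What the plan says.** Section 14.2.1 has three layers.

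- **Lead-in.** It restricts what must go to the IRB: "Only adverse events that the Sponsor determines to be serious, unanticipated, and related or possibly/probably (i.e., more likely than not) related to the research". It then names the recipients: "Those adverse events will be submitted in the applicable IRB and sponsor, according the following guidelines".
- **Three deadlines.** The first is "Report within 24 hours of learning about any subject's death that was unanticipated and more likely related to the research than unrelated". The second is "Report within 5 business days of learning about any serious, unanticipated, and related or possibly/probably related adverse event", followed by a closing condition that a relation to the research must be the likelier alternative. The third is "Report within 10 business days of learning about any other SAE that does not meet the above criteria".
- **A separate duty on the Principal Investigator.** "each study treatment-related serious adverse event will also be reported to BioMimetix JV, LLC, within 24 hours". This sentence sets no condition on expectedness or on degree of likelihood.

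The same section makes the sponsor responsible for FDA safety reports. The limit is 15 days, or 7 days for unexpected fatal or life-threatening suspected reactions. Before submitting, the sponsor must confirm that there is a reasonable possibility of a causal link.

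Other sections use attribution terms differently. Section 14.1 has a five-level scale on which *possible* means only that the drug may be the cause. Section 11.11 sets the DLT threshold at events "at least (possibly, probably, or definitely) attributable to BMX-001 during the study". Sections 16.1.5.3 and 16.2.2.1 include possible events when they summarise treatment-related AEs.

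**The concern.** The sponsor is assigned the relatedness judgement and the FDA decision, so it needs to receive serious events before anyone has screened them out on causality. Section 14.2.1 does the reverse for some events: the only fast route to BioMimetix is open to SAEs already regarded as treatment-related. An SAE rated unlikely or unrelated falls to the slowest deadline on a list whose opening words exclude it altogether.

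A single site sees few patients and may call an event unrelated that would look different beside similar events at other sites. The documents themselves report grade 3 hypotension and tachycardia at a 42 mg load in the glioma trial (4.2), and QTc prolongation after loading in 3 of 40 subjects across trials (11.10.4). Late receipt of a cardiovascular event or an unexplained death would therefore matter.

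**Working it through.** This is a check of wording; the plan states no figure to reproduce.

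**Step 1: the lead-in against the third deadline.** The lead-in admits only events that are serious, unanticipated and related in the sponsor's determination. The third deadline applies to SAEs that fail those tests. Both cannot govern one list.

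**Step 2: two meanings of possible.** The lead-in treats possibly and probably as more likely than not. Section 14.1 has separate levels for *possible* (may be related) and *probably* (likely related). An unanticipated SAE rated *possible* can therefore satisfy the opening words of the second deadline and fail its closing condition. It then drops to the third.

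**Step 3: the deadlines by rating**, for an unanticipated SAE:

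| Rating on the 14.1 scale | List to IRB and sponsor | PI to BioMimetix |
|---|---|---|
| Definite or probable, death | 24 hours | 24 hours |
| Definite or probable, not fatal | 5 business days | 24 hours |
| Possible, and not judged likelier than not | 10 business days | 24 hours if *treatment-related* includes possible; otherwise none |
| Unlikely or unrelated, including death | 10 business days | none |

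The first deadline does not rescue the last row, because it covers only deaths more likely related than not. Section 14.1.1 does not either: it gives BioMimetix regular notice of treatment-related AEs only. The closing sentence of 14.2.1, on serious and unexpected AEs, goes to the IRB under local guidelines, not to the sponsor.

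**Step 4: business days to calendar days**, ignoring public holidays.

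- Awareness on a weekday: 10 business days = 2 weeks = 14 calendar days.
- Awareness on a Saturday: 14 − 1 = 13 days. On a Sunday: 14 − 2 = 12 days.
- Range: 12 to 14 calendar days, against 1 day under the BioMimetix sentence. For 5 business days the same steps give 7, 6 and 5, so 5 to 7 calendar days.

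**Step 5: against the FDA limits.** The section does not say when the 7- and 15-day periods start. If they ran from site awareness (an assumption), the 12 to 14 days would exceed the 7-day limit by 5 to 7 days and leave 15 − 14 = 1 to 15 − 12 = 3 days of the longer one. If they ran from sponsor receipt, no limit would be broken, but the sponsor's assessment would still begin 12 to 14 days after the site knew.

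**The case against.** The strongest reply is that the three deadlines are tiers for different events, the third being residual, and that the BioMimetix sentence adds to them. A site that follows the stricter rule satisfies both. For a possibly related SAE at DLT level this reply largely stands. The 24-hour sentence carries no likelihood test, Section 16 counts possible as treatment-related, and a DLT is by definition at least possibly attributable. Such an event is probably caught within 24 hours, though 14.2.1 does not define the term. For an SAE rated unlikely or unrelated the reply fails, because the additional duty does not reach it.

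A reader might infer more than the text supports:

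- *That reports may arrive after 10 business days.* The wording is within, so 10 business days is the outer limit.
- *That the investigator's causality call outranks the sponsor's.* The written gate is the sponsor's determination. Section 14.2 names the investigator's opinion for seriousness only, and 14.2.1 does not say whose relatedness call triggers the 24-hour duty. Because the Principal Investigator must act on it within a day, the site's view will come first in practice, but that is an inference.
- *That a possible rating delays the lead-in pause or the DSMB notice.* The pause in 4.3.2 needs a definite relation and the 48-hour notice in 14.3 a probable or definite one. A possible rating triggers neither, however fast it is reported.
- *That a fixed number of further doses is given meanwhile.* That would assume last-day reporting and no interruption of treatment.

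It can also be said that reporting every SAE within 24 hours is a new policy that no section requires. That is true. It is recommended because the sponsor is given a judgement it cannot make on events it has not received.

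**Conclusion.** Section 14.2.1 is internally inconsistent, and the consequence goes beyond untidy wording. An SAE regarded at the site as unlikely or unrelated, including an unexpected death, has no 24-hour route and may compliantly reach the sponsor as late as 10 business days, that is 12 to 14 calendar days, after awareness. For an SAE rated possible, the limit is 24 hours if *treatment-related* includes possible, and otherwise up to 10 business days.

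This rests on two assumptions. First, BioMimetix is taken to be the sponsor, as its medical monitor's role in 11.10.4 and its monitoring role in 14.4 suggest. If the sponsor were another entity, the list would be its only dated route for site reports. Second, public holidays are ignored. No breach of an FDA limit is claimed, since the start of those periods is not stated. Nothing is built on the SAE contact in 14.2, whose identity is removed from the public copy.

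**What to change.** Amend 14.2.1 as follows.

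1. Separate site-to-sponsor reporting from IRB reporting.
2. Require every SAE, whatever its attribution, to reach the sponsor within 24 hours of site awareness, so that the sponsor can make the relatedness determination.
3. Keep the IRB timelines as their own list, and reconcile its opening restriction with the third deadline: either the list is limited to qualifying events or it covers the rest as well.
4. Delete the gloss that equates possibly with more likely than not. Use the five-level scale of 14.1 and state that *treatment-related* includes *possible*, in line with 11.11 and Section 16.

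The cost is amendment wording and modestly more SAE forms sent to the sponsor. No treatment rule, endpoint or sample size changes. If the IRB threshold is meant to stay at more likely than not, the IRB list can say so directly without redefining possible.

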14.3 External Data and Safety Monitoring Board (DSMB)

The sponsor and Principal Investigators are responsible for overseeing the safety and efficacy of the trial, executing the DSM plan, and complying with all reporting requirements to local and federal authorities. Additional oversight will be carried out by an external DSMB.

An external DSMB will be utilized to monitor the Phase 1/Phase 2 clinical trial of BMX-001. This DSMB will be organized to meet requirements of Western IRB, the institutional IRBs, and the NCI. We anticipate a charter with a minimum of 3 members, which may include: a radiation oncologist, a medical oncologist both with expertise in head and neck cancer, a biostatistician, and/or an ethicist or patient advocate. The DSMB will hold an initial meeting to review the final protocol before enrollment of the first patient. The responsibilities of the DSMB will be to review safety of study procedures, to maintain study integrity, to review adverse events and to review efficacy of the outcome data. The DSMB will meet either face to face or by teleconference at least semi-annually and on an ad hoc basis as indicated by any adverse events. Minutes will be kept of both open and closed meetings of the DSMB. At the end of the study, all minutes taken will be available to the clinical trial principal investigators, the NCI, and BioMimetix JV, LLC.

During Phase 2 of the trial, the sponsor will notify the DSMB within 48 hours of any reported grade 3-5 DLT deemed probably or definitely related to BMX-001.

The DSMB's responsibilities will include evaluation of treatment outcome for evidence of tumor protection by the study drug. If the DSMB determines that there is substantial evidence of excess tumor progression in the presence of the study drug, the DSMB will have authority to recommend closure of the clinical trial.

14.4 Monitoring

BioMimetix JV, LLC, will be responsible for oversight of monitoring the trial per the trial monitoring plan and will conduct monitoring visits to ensure subject safety and to ensure that the protocol is conducted, recorded, and reported in accordance with the protocol, standard operating procedures, good clinical practice, and applicable regulatory requirements.

Monitoring visits will be conducted in compliance with FDA regulations (21CFR812), SOPs, and GCP/ICH (5.18) guidelines to ensure the integrity of the data reported is accurate and the safety, rights, and well-being of the subjects are protected. The clinical trial will be monitored while the trial is active and is enrolling and overseeing patients.

Additional monitoring may be prompted by findings from monitoring visits, unexpected frequency of serious and/or unexpected toxicities, or for cause. Every reasonable effort will be made to maintain confidentiality during study monitoring.

14.5 Audits

The clinical centers may conduct internal audits to evaluate compliance with the protocol and the principles of GCP. The PIs agree to allow auditors direct access to all relevant documents and to allocate his/her time and the time of the study team to the auditors in order to discuss findings and any relevant issues.

The primary purpose of the audit is to verify that the standards for safety of human subjects in clinical trials and the quality of data produced by the clinical trial research are met. The audit will serve as a quality assurance measure, internal to the institution. Additional goals of such audits are to detect both random and systemic errors occurring during the conduct of clinical research and to emphasize "best practices" in the research/clinical trials environment.

15 Data Management and Processing

15.1 Study Documentation

Study documentation includes but is not limited to source documents, case report forms, monitoring logs, appointment schedules, study team correspondence with sponsors or regulatory bodies/committees, and regulatory documents that can be found in the study-specific regulatory binder, which includes but is not limited to signed protocol and amendments, approved and signed informed consent forms, FDA Form 1572, CAP and CLIA laboratory certifications, and clinical supplies receipts and distribution records.

Source documents are original records that contain source data, which is all information in original records of clinical findings, observations, or other activities in a clinical trial necessary for the reconstruction and evaluation of the trial. Source documents include but are not limited to hospital records, clinical and office charts, laboratory notes, memoranda, subjects' diaries or evaluation checklists, pharmacy dispensing records, recorded data from automated instruments, copies or transcriptions certified after verification as being accurate copies, microfiches, photographic negatives, microfilm or magnetic media, x-rays, subject files, and records kept at the pharmacy, at the laboratories and at medico-technical departments involved in the clinical trial. When possible, the original record should be retained as the source document. However, a photocopy is acceptable provided that it is a clear, legible, and an exact duplication of the original document.

15.2 Case Report Forms (CRFs)

The electronic CRF (eCRF) will be the primary data collection document for the study and is developed in conjunction with statistical oversight. The CRFs will be updated in a timely manner following acquisition of new source data. Only the staff appropriately delegated by the PI are permitted to make entries, changes, or corrections in the eCRF.

An audit trail will be maintained automatically by an electronic CRF management system. All users of this system will complete user training, as required or appropriate per regulations.

15.3 Data Management Procedures and Data Verification

Users of the eCRF will have access based on their specific roles in the protocol.

Completeness of entered data will be checked automatically by the eCRF system, and users will be alerted to the presence of data inconsistencies. Additionally, the data management team and the statistical team will cross-reference the data to verify accuracy. Missing or implausible data will be highlighted for the PI requiring appropriate responses (i.e., confirmation of data, correction of data, completion or confirmation that data is not available, etc.).

The database will be reviewed and discussed prior to database closure and will be closed only after resolution of all remaining queries. An audit trail will be kept of all subsequent changes to the data.

15.4 Coding

All medical terms will be coded using CTCAE v.4.03, which has been harmonized to MedDRA (Medical Dictionary for Regulatory Activities) coding. Medication will be coded according to the World Health Organization Drug Dictionary.

15.5 Study Closure

Following completion of the studies, the PI will be responsible for ensuring the following activities:

- Data clarification and/or resolution;
- Accounting, reconciliation, and destruction/return of used and unused study drugs;
- Review of site study records for completeness;
- Shipment of all remaining laboratory samples to the designated laboratories;
- Submitting closure report to IRB.

15.6 Records Retention

The Principal Investigator will maintain study-related records for the longer of a period of:

- at least two years after the date on which a New Drug Application is approved by the FDA, as an IND is involved;
- at least two years after formal withdrawal of the IND associated with this protocol, as an IND is involved;
- per institutional guidelines.

16 Statistical Methods and Data Analysis

All statistical analysis will be performed under the direction of [name]., University of Nebraska Medical Center (UNMC). Any data analysis carried out independently by the investigator must be approved by the lead statistician before publication or presentation.

All patients who receive protocol treatment are expected to be included in all statistical analyses. In Phase 1, cohorts of 3 patients will be treated starting with dose level #1 and ending with dose level #2. Once three patients have undergone treatment without experiencing DLT after a monitoring period of four weeks, the dose of the subsequent group of 3 patients will be escalated. Phase 1

16.1.1 Analysis Sets

All patients who receive protocol treatment are expected to be included in all statistical analyses.

For purposes of determining dose escalation, we expect that all patients will be included in analyses with the possible exception of those patients receiving treatment who refuse to return for assessment and for whom information concerning toxicity cannot be garnered from other sources (e.g., primary care physician, family members, etc).

For adverse events, overall survival and progression free survival, all patients who receive BMX-001 will be included in the summaries of adverse events.

For HRQoL, all patients who receive BMX-001 will be included in the analysis with the possible exception of those patients receiving treatment who refuse to return for assessment and for whom HRQoL data are not available.

16.1.2 Patient Demographics and Other Baseline Characteristics

The clinical and sociodemographic characteristics of all patients treated will be summarized using descriptive statistics (e.g., means/standard deviations, percentiles, frequencies). Patient characteristics within patient subgroups defined by dose level will also be generated.

16.1.3 Treatments

The number of patients treated at each dose level will be summarized.

